1. OBJECTIVES

The objective of this study is to determine whether the opioid antagonist naltrexone reduces radiation therapy-related fatigue more than placebo does in patients undergoing radiotherapy for breast cancer.

[figure not shown]
1.1 Study Design

A randomized, double-blind, parallel-arm 5-week clinical trial will be used to determine the effect of naltrexone on fatigue emerging during radiation therapy for non-metastatic breast cancer (see Protocol Schema). The trial has two phases (a monitoring phase and an intervention phase) requiring two separate consents.

Monitoring phase: Prior to initiating radiotherapy, participants will be approached and consented for the monitoring phase of the study, which involves longitudinal monitoring of fatigue in order to establish whether a patient develops fatigue after starting radiation. The level of pre-radiotherapy fatigue will be obtained during the final 3 weeks before, or within 3 days, that radiotherapy is started. Participants who provide baseline data and report suicidal ideation either spontaneously or on a self-report questionnaire will be excluded from subsequent weekly monitoring of fatigue. All other participants will undergo weekly monitoring of fatigue via a brief self-report questionnaire (Functional Assessment of Chronic Illness Therapy-Fatigue Subscale; FACIT-F) once radiation therapy begins. Those whose fatigue symptoms increase above the pre-specified threshold at any point during the monitoring period will be approached about enrollment into the intervention phase of the study. The monitoring period will continue up until one month after the conclusion of radiotherapy. Radiation oncologists will refer potentially eligible patients to the monitoring phase of the study. The clinical research coordinator will be trained to administer the screening consent and will follow participants during the monitoring phase of the study and notify the radiation oncologist if fatigue emerges/worsens after radiation therapy has begun, so that participation in the intervention phase of the study can be discussed with these patients.

Intervention phase: Radiation oncologists will consent patients who develop treatment-emergent fatigue developing during or within one month after completion of radiation therapy and who are interested in participating in the intervention phase of the study. After informed consent is obtained and final eligibility determination is complete, participants will have 5 study visits: one at study entry to initiate treatment (week 0), one to rule out any contraindication to the scheduled dose escalation (week 1), one at the conclusion of medication treatment for treatment outcome assessment and safety monitoring (week 5), and the last at four weeks after discontinuation of study drug vs. placebo (week 9). All intervention visits have a window of ± 7 days.

Study treatment: The treatment schedule includes a daily dose of double-blinded naltrexone vs. placebo for 5 weeks. Treatment will be initiated at 25 mg/day (or equivalent placebo) during the first week to improve tolerability. The dose will be escalated to 50 mg/day (or equivalent placebo) after one week barring significant early improvement in fatigue or adverse events precluding dose escalation, and participants will continue to take 50 mg/day (or 25 mg/day if dose is not escalated) for 4 weeks to complete a 5-week treatment period.

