The durations of most placebo-controlled trials of naltrexone for alcohol and opioid dependence have ranged from 12-52 weeks, although shorter positive trials (3-12 weeks) exist in the literature. Clinically, for treatment of alcohol and opioid dependence, an initial 4-month course of naltrexone is recommended, and the medication can be continued indefinitely in the setting of good response.²⁶ The present study differs in that the target population will receive naltrexone for radiotherapy-emergent fatigue, which has been shown in prior studies to improve spontaneously after the conclusion of radiation treatment, returning to pre-treatment levels in the majority of patients by three months after radiotherapy.^{13,15} Therefore, a 5-week trial duration will be utilized in order to minimize the possibility of missing the appropriate time period in which to demonstrate treatment effect as opposed to spontaneous recovery. Further supporting the 5-week trial duration is the observation that patients often demonstrate therapeutic benefit from naltrexone within the first few days or weeks of treatment.²⁷

Pharmacokinetics

Naltrexone has a volume of distribution of 1350 L, and is 21% protein bound. It is metabolized hepatically via dihydrodiol dehydrogenase and conjugation to its principal metabolite, 6-beta-naltrexol. It is 53-75% renally excreted, mostly as metabolites, less than 2% unchanged. The elimination half-life of 6-beta-naltrexone is 5-10 days.

Despite its hepatic metabolism, naltrexone does not interact with the cytochrome P450 enzyme system.

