- Visit 3 (five weeks after initiating study drug vs placebo): complete follow-up fatigue, anxiety, depression, sleep and quality of life questionnaires; review of concomitant medications; return medication bottles and diaries. Blood draw for LFTs.

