5.5 Duration of Therapy

Duration of therapy will be five weeks. In the absence of adverse event(s), treatment will continue for the entire five weeks unless one of the following criteria applies:

- Initiation of opioid-containing medications
- Intercurrent illness that prevents further administration of treatment
- Unacceptable adverse event(s)
- Participant demonstrates an inability or unwillingness to comply with the oral medication regimen and/or documentation requirements
- Participant decides to withdraw from the study
- General or specific changes in the participant's condition render the participant unacceptable for further treatment in the judgment of the treating investigator

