7.1 Naltrexone

7.1.1 Description

Naltrexone (a pure opioid antagonist) is a cyclopropyl derivative of oxymorphone similar in structure to naloxone and nalorphine (a morphine derivative). The chemical name is N-Cyclopropylmethylnoroxymorphone and the formula is $C_{20}H_{23}NO_4$. The molecular weight is 341.40092. The NIM PubChem Compound ID is 5360515. Pharmacokinetic information follows below:

Duration: Oral: 25-50 mg: 24 hours

Absorption: Oral: Almost complete

Distribution: V_d : ~1350 L; widely throughout the body but considerable interindividual variation exists

Metabolism: Extensively metabolized via noncytochrome-mediated dehydrogenase conversion to 6-beta-naltrexol (primary metabolite) and related minor metabolites; glucuronide conjugates are also formed from naltrexone and its metabolites

Oral: Extensive first-pass effect

Protein binding: 21%

Bioavailability: Oral: Variable range (5% to 40%)

Half-life elimination: Oral: 4 hours; 6-beta-naltrexol: 13 hours; I.M.: naltrexone and 6-beta-naltrexol: 5-10 days (dependent upon erosion of polymer)

Time to peak, serum: Oral: ~60 minutes; I.M.: Biphasic: ~2 hours (first peak), ~2-3 days (second peak)

Excretion: Primarily urine (as metabolites and small amounts of unchanged drug)

Despite its hepatic metabolism, naltrexone does not interact with the cytochrome P450 enzyme system.

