9. STUDY CALENDARS

*Note that study visits in both monitoring and intervention phase can be completed within 7 days of the scheduled date.

**Study measures, type of procedure, and study visit schedule
Monitoring Phase (6-week radiation therapy schedule)**

	Type	Baseline Visit	Weekly Monitoring Visits from Start of Radiation Therapy	Meets Fatigue Eligibility Threshold
Background Information Consent Demographics/Patient Characteristics Form Clinical Variables ^a	Self-report	X X	X ^a	
Fatigue FACIT-Fatigue Subscale PGI-F	Self-report Self-report	X ^b X ^b	X	X
Sleep PSQI ISI ESS Berlin Questionnaire	Self-report Self-report Self-report Self-report	X ^b X ^b X ^b X ^b		
Other Target Symptoms GAD7 PHQ9 FACT-B/FACT-ES CPFQ PEG	Self-report Self-report Self-report Self-report Self-report	X ^b X ^b X ^b X ^b X ^b	X ^c X ^c	
Safety monitoring Urine β -HCG LFTs ^d BUN/Creatinine ^d Hematocrit ^d TSH ^d				X X X X X
Subject Exit form (if applicable)				X ^e

a. Clinical Variables form completed once at end of radiation treatment for every patient in monitoring phase

b. baseline questionnaires to be completed within ≤ 21 days prior to, or within 3 days of starting radiation therapy, otherwise they need to be repeated.

c. During final week of RT, and 4 weeks after completion of RT

d. LFTs, BUN/Creatinine, Hematocrit will be accepted if drawn within 30 previous day; TSH within 6 months.

e. To be completed by study coordinator at time when patient is taken off-study for any reason. If patient continues on to Intervention Phase, this form will be completed when taken off intervention phase.

**Study measures, type of procedure, and study visit schedule
Monitoring Phase (Partial Breast Irradiation (PBI))**

	Type	Baseline Visit	Monitoring Visits	Meets Fatigue Eligibility Threshold
Background Information				
Consent		X		
Demographics/Patient Characteristics Form	Self-report	X		
Clinical Variables ^a			X ^a	
Fatigue				
FACIT-Fatigue Subscale	Self-report	X ^b	X ^c	X
PGI-F	Self-report	X ^b		
Sleep				
PSQI	Self-report	X ^b		
ISI	Self-report	X ^b		
ESS	Self-report	X ^b		
Berlin Questionnaire	Self-report	X ^b		
Other Target Symptoms				
GAD7	Self-report	X ^b		
PHQ9	Self-report	X ^b	X ^d	
FACT-B/FACT-ES	Self-report	X ^b	X ^d	
CPFQ	Self-report	X ^b		
PEG	Self-report	X ^b		
Safety monitoring				
Urine β -HCG				X
LFTs ^e				X
BUN/Creatinine ^e				X
Hematocrit ^e				X
TSH ^e				X
Subject Exit form (if applicable)				X ^f

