f. To be completed by study coordinator at time when patient is taken off-study for any reason. If patient continues on to Intervention Phase, this form will be completed when taken off intervention phase.

Study measures, type of procedure, and study visit schedule
Intervention Phase

	Week 0 Randomi zation Visit	Week 1 Rx Visit (+/- 7 days)	Week 5 Rx Visit (+/- 7 days)	Week 9 Follow- up Visit (+/- 7 days)
Background Information				
Consent	X			
Fatigue				
FACIT-Fatigue Subscale	X	X	X	X
PGI-I	X		X	
Sleep				
PSQI	X		X	
ISI	X		X	
ESS	X		X	
Berlin Questionnaire			X	
Other Target Symptoms				
GAD7	X		X	
PHQ9	X		X	
FACT-B/FACT-ES	X		X	
CPFQ	X		X	
PEG	X		X	
Safety monitoring				
LFTs			X	
Concomitant medications	X	X	X	
Adverse Events assessment		X	X	
Health status/life events review				X
Dispense medication	X	X		
Review medication diary	X	X	X	
Study Summary				
Subject Exit form				X ^a
Study Visit duration (min)	40	15	40	15

a. To be completed by study coordinator at time when patient is taken off-study for any reason.

Effect measures listed in the Table of Procedures are described below. In addition to these effect measures, we will examine potential covariates that may play a role in the evolution of fatigue during breast radiotherapy. These include radiotherapy related characteristics such as breast volume; type of radiotherapy (e.g. fractionation schedule, number of fields, design of tangent fields [e.g. partial vs. full breast irradiation], boost dose [mini-tangents vs. electrons]. Exercise type/frequency and travel time to clinic will be assessed, as these parameters have correlated with radiotherapy-emergent fatigue in prior studies³⁹. Finally, hematocrit will be measured at baseline.

The related symptom measure of obstructive sleep apnea will be evaluated via the Berlin Questionnaire and Epworth Sleepiness Scale:

Berlin Questionnaire (BQ): (Time: 2 minutes) The BQ will be done once at the beginning of the

study. It is an instrument used to identify patients at high risk for sleep apnea based on symptoms related to snoring and daytime sleepiness along with the presence of hypertension or obesity. It has been found to have high sensitivity and specificity in a primary care setting.⁴⁰

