3. Worrying too much about different things?

- 0 = not at all
- 1 = several days
- 2 = more than half the days
- 3 = nearly everyday

4. Trouble relaxing?

- 0 = not at all
- 1 = several days
- 2 = more than half the days
- 3 = nearly everyday

5. Being so restless that it is hard to sit still?

- 0 = not at all
- 1 = several days
- 2 = more than half the days
- 3 = nearly everyday

6. Becoming easily annoyed or irritable?

- 0 = not at all
- 1 = several days
- 2 = more than half the days
- 3 = nearly everyday

7. Feeling afraid as if something awful might happen?

- 0 = not at all
- 1 = several days
- 2 = more than half the days
- 3 = nearly everyday

If you checked off any problems, how difficult have these problems made it for you to do your work, take care of things at home, or get along with other people?

(Please circle one option below)

- Not difficult at all
- Somewhat difficult
- Very difficult
- Extremely difficult

Patient Initials/Signature: _____

Date: _____

Functional Assessment of Chronic Illness Therapy (FACIT) Fatigue Scale (Version 4)

Below is a list of statements that other people with your illness have said are important. Please circle or mark one number per line to indicate your response as it applies to the past 7 days.

		Not At All	A Little Bit	Somewhat	Quite a Bit	Very Much
1	I feel fatigued	0	1	2	3	4
2	I feel weak all over	0	1	2	3	4
3	I feel listless ("washed out")	0	1	2	3	4
4	I feel tired	0	1	2	3	4
5	I have trouble starting things because I am tired	0	1	2	3	4
6	I have trouble finishing things because I am tired	0	1	2	3	4
7	I have energy	0	1	2	3	4
8	I am able to do my usual activities	0	1	2	3	4
9	I need to sleep during the day	0	1	2	3	4
10	I am too tired to eat	0	1	2	3	4
11	I need help doing my usual activities	0	1	2	3	4
12	I am frustrated by being too tired to do the things I want to do	0	1	2	3	4
13	I have to limit my social activity because I am tired	0	1	2	3	4

Scoring: Items are scored as follows: 4=Not At All; 3=A Little Bit; 2=Somewhat; 1=Quite A Bit; 0=Very Much, EXCEPT items #7 and #8 which are reversed scored. Score range 0-52. A score of less than 30 indicates severe fatigue. The higher the score, the better the quality of life.

Item Number	Reverse Item?		Item Response	Item Score
1	4	-		=
2	4	-		=
3	4	-		=
4	4	-		=
5	4	-		=
6	4	-		=
7	0	+		=
8	0	+		=
9	4	-		=
10	4	-		=
11	4	-		=
12	4	-		=
13	4	-		=

Sum individual item scores: _____
 Multiply by 13: _____
 Divide by number of items answered: _____

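### The symmetric ±7 day window on the week-5 visit lets days after the last dose into the 7-day recall of the primary FACIT-F

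*Combined protocol and SAP*

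**What the plan says.** Section 5.5 fixes treatment length: "Duration of therapy will be five weeks". The appended medication diary ends at Day 35. Section 5.3 places the outcome visit at the same point ("Visit 3 (five weeks after initiating study drug vs placebo"), and Section 1.1 describes it as the treatment-outcome visit at the conclusion of medication.

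The tolerance around that visit is stated more than once. Section 1.1 says "All intervention visits have a window of ± 7 days". The general note to Section 9 says "study visits in both monitoring and intervention phase can be completed within 7 days of the scheduled date", and the intervention calendar repeats the ± 7 days in its week-5 column.

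The appended FACIT Fatigue form tells patients to "indicate your response as it applies to the past 7 days".

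On persistence of the drug, Section 7.1.1 gives "Duration: Oral: 25-50 mg: 24 hours", with oral half-lives of 4 hours for naltrexone and 13 hours for its metabolite. Section 2.2 states, without naming a route, "The elimination half-life of 6-beta-naltrexone is 5-10 days"; Section 7.1.1 gives 5-10 days for the intramuscular form.

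Nothing in the documents requires the week-5 FACIT-F to be answered while drug is still being taken, extends dosing to a late visit, or treats a late in-window score differently in the analysis.

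**The concern.** The window is symmetric, but its two sides differ. For a patient who completes treatment, a visit on days 28-35 asks about a week on study drug. A visit on days 36-42 asks about a week that lies partly, and at the far edge almost or entirely, after the last dose. Both are compliant and both enter the primary outcome on equal terms.

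If benefit fades once dosing stops, late scores pull the arms together and raise the chance of missing a real effect. The spread also adds noise: Section 2.2 expects fatigue to recover by itself after radiotherapy, and gives that as the reason for a 5-week trial. A score that may be taken anywhere in a 15-day range sits awkwardly with that reasoning. A score collected late cannot be moved back afterwards.

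**Working it through.** **Inputs.** Last dose day 35 (Section 5.5, diary). Permitted visit days 28 to 42 (Sections 1.1, 5.3, 9). Recall 7 days (FACIT form). Difference 3.6 points, SD 10, two-sided 0.05, 122 per arm (Section 12).

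**Plan's own figure.** The standard error of the difference is 10 × √(2/122) = 1.280. Then 3.6/1.280 = 2.812, and power = Φ(2.812 − 1.960) = 0.803. The stated 122 per arm for 80% power is reproduced.

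**Post-dose recall days for a visit on day d.** If the visit day counts as a recall day, the recall covers d−6 to d, and the post-dose days number max(0, d−35). If it does not, the recall covers d−7 to d−1, and they number max(0, d−36).

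| Visit day | Visit day counted | Not counted |
|---|---|---|
| 28-35 | 0 of 7 | 0 of 7 |
| 36 | 1 | 0 |
| 38 | 3 | 2 |
| 40 | 5 | 4 |
| 42 | 7 | 6 |

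This places the nominal visit on day 35. If five weeks after a day-1 first dose is read as day 36, the latest visit is day 43 and 7 of 7 recall days are post-dose under either count.

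**Drug remaining, from Section 7.1.1.** With a 13-hour half-life, the metabolite left is 0.5^(24/13) = 28% at 24 hours, 0.5^(72/13) = 2% at 72 hours and 0.5^(168/13) = 0.01% at 7 days. With the 5-10 days in Section 2.2, it would be 0.5^(7/5) = 38% to 0.5^(7/10) = 62% at 7 days.

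**Illustrative power.** Assumptions, neither of them in the documents: the effect is proportional to the share of recall days up to the last dose, and visits are spread evenly over the range shown. Effect = 3.6 × share; power = Φ(effect/1.280 − 1.960).

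| Visit days | Share, visit day counted | Effect | Power | Share, not counted | Effect | Power |
|---|---|---|---|---|---|---|
| 32-38 | (7 − 6/7)/7 = 88% | 3.16 | 69% | (7 − 3/7)/7 = 94% | 3.38 | 75% |
| 28-42 | (7 − 28/15)/7 = 73% | 2.64 | 54% | (7 − 21/15)/7 = 80% | 2.88 | 61% |
| 35-42 | (7 − 28/8)/7 = 50% | 1.80 | 29% | (7 − 21/8)/7 = 62.5% | 2.25 | 42% |

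**Carryover.** With the visit day counted, one further day of full effect after the last dose gives the same figures as the right-hand columns. Three further days give 80%, 72% and 64%.

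**The case against.** A reader might infer that the primary outcome is wholly off drug within protocol. The documents do not support that as a general statement. Wholly post-dose recall needs a visit on day 42, one of 15 permitted days, and needs the visit day to be counted; otherwise day 42 still includes one dosing day. The visit is scheduled for the end of medication, and ±7 days is a tolerance around that target. This stands, and it limits the point to partial dilution.

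A reader might also take 54% or 29% as the trial's real power. That is not supported either. No section gives the distribution of visit days or says how quickly fatigue returns. Section 7.1.1 describes the drug's persistence, not the persistence of benefit. The 29-42% row needs every visit to fall on days 35-42.

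Nor do the objectives ask for an effect while the receptor is blocked. Sections 1 and 1.2 ask whether naltrexone reduces fatigue more than placebo does; blockade is the rationale in Section 2.

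Finally, the primary time point is not firmly fixed. Section 12.1 says only the end of the study, Sections 10 and 12 refer to a follow-up FACIT, and the calendar collects the scale at weeks 5 and 9. Section 1.1 supports week 5. If week 9 were meant, the outcome would be about four weeks after dosing by design and this window would not matter. That ambiguity has to be settled first.

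None of this removes the core: the day count follows from the text, and no rule limits or adjusts for late scores.

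**Conclusion.** The point holds in a limited form. An in-window visit after day 35 can bring post-dose days into the primary FACIT-F, up to 6 or 7 of 7 at day 42. On the figures in Section 7.1.1 this can dilute the contrast between arms and add noise from spontaneous recovery. The window is the same in both blinded arms, so it does not by itself inflate type I error; the risk is a false negative.

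Confidence is high for the day count and low for the size. The power figures show a range under the stated assumptions and are not estimates: tight scheduling with three days of carryover leaves power at 80%, and later visits with no carryover lower it materially. The conclusion takes week 5 as the primary time point. It would weaken if the longer half-life in Section 2.2 applied to the oral form, so that conflict with Section 7.1.1 must be reconciled. The change is worth making because it is cheap and late scores cannot be repaired.

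**What to change.** 1. Name week 5 as the primary time point in Section 12.1, and use the same wording in Sections 10 and 12.
2. In Sections 1.1, 5.3 and 9, set the target window for the week-5 FACIT-F and the other week-5 questionnaires to end on the last scheduled dosing day, for example days 29-35. Allow phone completion, which Section 5.3 already permits in the monitoring phase. Keep ±7 days for the clinic visit, bottle return and LFTs.
3. Record the last-dose date and the FACIT-F date for every patient.
4. State in Sections 12.1 and 12.5.2 that a FACIT-F completed after the target window but within the existing ±7 days, or after early stopping of drug, is still collected, stays in the primary analysis and is not a reason for exclusion. Without this, the completers-only analysis set could turn a day-36 score, compliant today, into an exclusion.
5. Pre-specify a sensitivity analysis limited to FACIT-Fs completed on treatment.
6. Separately, reconcile the metabolite half-lives in Sections 2.2 and 7.1.1.

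The cost is a few lines of text, a narrower target for one set of questionnaires and some phone calls. Dosing and sample size do not change.

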1.2 Primary Objectives

To determine the effect of naltrexone on treatment-emergent fatigue during radiation therapy for breast cancer. The primary comparison is between changes in fatigue scores in the naltrexone-versus the placebo-treated participants as measured by the FACIT-F subscale.

1.3 Secondary Objectives

1.3.1. To determine the effect of naltrexone on exploratory outcomes including: mood, anxiety, subjective cognitive function, sleep, pain, and quality of life, and the extent to which changes in fatigue correlate with changes in these symptom endpoints. These outcomes have been shown to be associated with cancer fatigue in prior studies involving breast cancer patients^{1 2-4}.

1.3.2. To determine the course, predictors, and correlates of fatigue during radiotherapy for breast cancer in a large controlled sample

2. BACKGROUND

2.1 Study Disease(s)

Fatigue is one of the most common side effects of both radiation therapy and chemotherapy. It is the greatest predictor of poor quality of life in cancer patients undergoing treatment, and very often results in an inability to perform activities of daily living easily accomplished prior to treatment (Hickok et al., 1996). More importantly, severe fatigue can result in breaks in treatment that adversely affect treatment efficacy and ultimately compromise survival.

Despite its importance as a side effect that impairs quality of life and reduces treatment adherence, treatment options for cancer-related fatigue are limited. Exercise programs and psychological interventions such as cognitive-behavioral therapy appear to have a positive effect on cancer-related fatigue⁵, but are not accessible or feasible for all patients who might benefit. In terms of pharmacologic strategies, a recent meta-analytic review suggested that stimulants (e.g., methylphenidate) and hematopoietic agents (the latter only in the presence of anemia) may be effective⁶. However, the effect size of stimulants, albeit clinically significant, is small; hematopoietic agents such as erythropoietin are less widely used given associated increase in risk for thrombovascular events and mortality. Modafinil and armodafinil, both non-amphetamine based stimulant-like medications that improve fatigue related to obstructive sleep apnea and multiple sclerosis, have been the focus of more recent randomized trials. Specifically, a Phase III trial in patients with a wide variety of cancer types found that modafinil has significantly positive effects for severe, but not mild to moderate, cancer fatigue⁷. Trial durations for effective pharmacological interventions in cancer fatigue are variable, ranging from 2-12 weeks, many of which show benefit with 4 weeks.⁶

Although their use is widespread, stimulants and stimulant-like medications may exert nonspecific effects that are not tied to an underlying cancer-related mechanism of fatigue. Some work has suggested that cancer fatigue may be driven by the activation of pro-inflammatory cytokines, paving the way for study of cytokine inhibitors such as etanercept, which in a study of advanced cancer patients on chemotherapy appeared to reduce fatigue⁸. Other proposed mechanisms include disruptions in the hypothalamic-pituitary-adrenal axis, as shown by studies revealing altered cortisol responses in fatigued cancer survivors⁹ and metastatic breast cancer patients¹⁰. However, at this point, there is limited direct clinical evidence to substantiate these theories. Thus, interventions to manage cancer-related fatigue continue to be empirical in nature, possibly accounting for their modest effect sizes.

The present study stems from a preclinical observation implicating upregulation of the endogenous opioid system as a potential underlying mechanism for fatigue in patients receiving radiotherapy. As in humans, irradiation (of the tail) has been shown to induce lethargy in rodent models and beta-endorphin levels increase in response to tail irradiation. [name] lab has observed that the opiate receptor antagonist naloxone reverses fatigue induced by irradiation. Preclinical data (further described in Section 2.3, Rationale) suggest that the elevations in beta-endorphin may be responsible for radiation-related fatigue, and that pharmacologic treatment with a mu-opioid receptor antagonist may ameliorate the fatigue symptoms. Thus, the primary aim of this study is to determine whether the widely used and FDA-approved opioid antagonist naltrexone might reduce radiation-emergent fatigue in humans.

Given results of pre-clinical studies, naltrexone is a viable treatment to investigate for

radiation-related fatigue in cancer patient populations who are not expected to require opioid therapy. Breast cancer patients receiving radiotherapy represent an important population to study because fatigue develops commonly during radiotherapy and concurrent therapy with opioids is rare. Notably, existing literature provides widely variable estimates (38-75%) of the prevalence of breast radiotherapy-emergent fatigue^{11,12} as well as differing evidence as to the most important predictors of fatigue in this population. Longitudinal studies have found that fatigue levels gradually increase during a course of breast radiotherapy, particularly during the first four weeks of treatment.¹³⁻¹⁵ Several studies have investigated clinical correlates of radiation-related fatigue in this population. Donovan found that patients (N=134) pre-treated with chemotherapy reported less fatigue during radiotherapy as compared to patients who did not receive chemotherapy, and that demographic and disease-related variables did not predict the extent of fatigue; however, psychological variables were not examined in this study.¹⁶ Manir described anemia as the most important predictor of fatigue (N=72)¹² whereas other studies have found no relationship between hemoglobin levels and fatigue.¹³ Recently, Taunk compared different radiotherapeutic regimens for early-stage breast cancer (overall N=80) and suggested that partial breast irradiation may reduce fatigue as compared to hypofractionated and standard whole breast irradiation.¹⁷ However, in the largest cohort study to date (N=250), Reidunsdatter identified medical comorbidity as a more important determinant of increased fatigue during breast radiotherapy than radiotherapy type.¹⁸ By contrast, Courtier reported that anxiety, elevated pre-treatment fatigue, and diagnoses other than invasive ductal carcinoma (e.g. DCIS or lobular subtypes) predicted radiation-emergent fatigue (N=100).¹¹ More study of the clinical correlates and course of fatigue during radiotherapy is warranted in the breast cancer population given the relatively small sample sizes, variable inclusion of relevant medical and psychosocial variables in models to predict fatigue, and conflicting findings to date. The monitoring phase of the present study offers an embedded opportunity to analyze the course, predictors, and correlates of radiotherapy-related fatigue in a controlled breast cancer population.

